mechanisms to remove thrombus, which are often impaired in children with DVT[27]. Even in those who achieve clot lysis, permanent damage to venous valves occurs frequently, likely via thrombus-induced activation of inflammation[14]. *I propose that a bidirectional relationship between inflammation and abnormal fibrinolysis drives a feedback loop resulting in increased complications after DVT over time, including PTS (Figure 1).*

Bringing together this insight and our current knowledge of coagulation assessment by global assays -focusing on PTS- may uncover new and better approaches to identify and treat at-risk individuals. Exercise has shown to decrease thrombin generation and fibrinolytic markers in children as well as adults. Alterations in the level of related biomarkers, reflecting coagulation activation, inflammation and markers of fibrinolysis, may be of interest when assessing a patient's risk of developing PTS.

Extrapolating from the above, I propose that an activity regimen for children after lower extremity DVT is unlikely to be harmful, maybe of benefit and needs further study. In the past, investigator initiated trials involving prevention or treatment of pediatric VTE have been terminated because of feasibility concerns[28]. Accordingly, a pilot study to establish feasibility of this approach is required before proceeding to a fully powered, definitive trial.

INNOVATION

This proposal is innovative because: (1) it will be the *first* trial to integrate modern technological tools, such as activity trackers to improve adherence to life style interventions aimed at preventing PTS. Although there are many ways to increase physical activity in children, my goal is to use a simple, user-friendly tool that will appeal to children across a broad age range; (2) activity/exercise as a therapeutic modality in children with DVT has not been previously studied; (3) there have been no previous randomized trials of PTS prevention or treatment in children; and (4) trial outcomes include patient reported outcomes (i.e. QoL) and laboratory based biomarkers.

PRIMARY AIM:

To demonstrate the feasibility and potential effectiveness of a personal “fitness tracker” to improve adherence to an activity regimen following an initial DVT in children.

[figure not shown]
Hypothesis: The intervention of using a fitness tracker to adhere to an activity regimen will be acceptable, and effective in improving adherence

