to a post-DVT activity regimen in children. I propose a validated, fitness tracker, the Fitbit, to improve adherence to a 16-week activity regimen in a pilot randomized controlled trial (RCT), in which 44 subjects with DVT will be assigned to the intervention group or to a comparison group. The primary outcomes will consist of a) feasibility indicators determined *a priori* (eligibility, consent, adherence, retention) and b) estimates of effect size associated with the prescribed activity regimen, by describing within-subject change in QoL and 'potential' biomarkers of PTS pre and post intervention in each group.

STUDY DESIGN (Figure 2)

The study design is that of a pilot RCT to test the feasibility of the proposed activity tracker to increase activity in children post DVT, against standard practice, which currently consists of providing education about PTS and instructions to 'be active'. I will use a validated activity tracker, the Fitbit and its data platform- the Fitabase.

METHODS

I. STUDY SETTING

All newly diagnosed patients with first, lower extremity DVT diagnosed at Children's Health System of Texas (CHST) or referred to the Hemostasis Thrombosis Center (HTC) at CHST who have completed 12 weeks (± 2 weeks) of anticoagulation therapy, will be approached for recruitment.

II. ELIGIBILITY CRITERIA

Parents must provide written, informed consent before any study procedures occur.

INCLUSION CRITERIA	RATIONALE
1. Age 7-21 years	VTE is seen across all age groups
2. A radiologically confirmed, acute, proximal (iliofemoral and femoropopliteal) first lower extremity DVT and/or confirmed,	Population with proximal DVT and/or PE deemed to be at highest risk of PTS

acute pulmonary embolism (unilateral or bilateral)	
3. 12 weeks (± 2 weeks) after starting anticoagulation	To mitigate the small theoretical risk of clot dislodgement with activity soon after DVT diagnosis
4. Out-patient ambulatory status	Protocol involves increasing activity

EXCLUSION CRITERIA	
1. Contraindication to increasing activity such as patients with juvenile arthritis, poor balance, congestive heart failure etc.	Protocol involves increasing activity

III. STUDY PROTOCOL

The study has 3-4 planned visits, which will coincide with the standard of care visits.

Screening

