The parents/legal guardians will be given an explanation about the study and informed consent and/or assent will be obtained. This may occur in the inpatient or the outpatient setting. Demographic information and relevant medical history, including results of scans and thrombophilia testing will be collected. All medications, including anticoagulant medication received for the thrombotic event will be recorded.

a. Baseline Assessments (collected as SOC (standard of care)):

i. History and Physical Examination:

1. Detailed history regarding medical disorders predisposing to thrombosis and potential triggers (birth control pills, recent travel or surgery or immobility) and predispositions (thrombophilia, obesity etc.) will be collected.
2. Review of existing medical records recorded on Children's Medical Center electronic medical record to review past medical, family and social history will be performed.
3. Comprehensive physical exam (PE) consisting of vital signs, general appearance, head, eyes,

ears, nose, throat (HEENT), cardio-respiratory, abdominal, extremities and skin will be performed at each visit as per standard of care.

- ii. Laboratory:
 - 1. Complete blood count (CBC), reticulocyte count, baseline coagulation studies, and a comprehensive thrombophilia panel performed as SOC will be recorded.
- iii. Treatment:
 - 1. Information on anticoagulant therapy (medication of choice, intensity of anticoagulation, planned duration of therapy) prescribed as per the treating physician will be collected for subjects who meet eligibility criteria and whose parents provide written informed consent
- iv. Radiological:
 - 1. All information related to site, extent and venous segments involved of the thrombotic venous segment at the time of diagnosis, and at completion of therapy will be collected. Information on reflux assessment at the time of end of therapy ultrasound will also be collected.
- v. Assessment of **Post-thrombotic syndrome (PTS)**: All subjects will be assessed with standardized, validated outcome assessment tools: the Manco-Johnson Instrument and the modified Villalta scale starting at 6 months post diagnosis of DVT as per standard of care. See appendix 1 for these scales.

b. Study Interventions:

i. Study procedures/Randomization:

Eligible, consenting subjects will be individually randomized via a web-based program to the Fitbit arm or the control arm (1:1 allocation ratio).

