- 1. **Intervention (Fitbit) arm.** The intervention arm will wear a Fitbit for a 16-week period (**Figure 2**). **General Principles of an aerobic activity regimen:**

As the principal muscles affected by PTS are the lower limb muscles, we have opted to use a walking-jogging program to capture steps/day by the Fitbit. This will target all potentially affected muscles (quadriceps, hamstrings and gastrocnemius/soleus). If preferred by the subject, other weight bearing exercises could replace the walk/jog, for example, dancing or team sports such as basketball or volleyball. Because of the unfamiliarity with activity trackers, subjects will be provided with hands-on training to promote successful use of the Fitbit and Fitabase.

a. Schedule and procedures (Table 1): After consent (baseline visit), subjects in this arm will receive a standardized 15-20 minute education session on PTS (what constitutes PTS, why patients get it, how to manage it) and enhanced activity after DVT. Subjects will be asked to wear the Fitbit for a period of four weeks to establish baseline or 'habitual' activity. Using steps/day data received at the end of four weeks, we will determine an individualized activity prescription of 'target steps/day', corresponding to a 25% increase above the baseline.

Table 1	Visit 1	Visit 2	Visit 3
	12 wks post DVT Dx (\pm 2 weeks)	16 wks after Visit 1 (\pm 4 weeks)	8 wks after Visit 2 (\pm 4 weeks)
	SOC Visit	SOC Visit	SOC Visit (Exit Visit)
ALL SUBJECTS			
Informed Consent	X*		
Full Medical History and Exam	X	X	
Biomarker Testing [^]	X\$	X	X
FXIII, D-dimer, CRP	X	X	X ^{^^}
QOL forms	X	X	X
PTS Assessment		X	X
ECS and Log	X	X~	X~
Activity Logs/ Questionnaire	X	X	X
Medication Log***	X	X	X

Phone Calls (monthly)	X	X	
Formal Education Session	X		
Honoraria**	X	X	X
SUBJECTS IN FITBIT ARM			
Hands on Fitbit Training	X		
Steps/Day Data (weekly)	X	X	X
Phone Calls (weekly)	X	X	
Return Fitbit			X

*Informed consent can occur any time after DVT diagnosis until Visit 1; ^Biomarker testing includes: D-Dimer, FVIII, Thrombin generation, markers of fibrinolysis; \$Biomarker testing at Visit 1 may be combined with other SOC labs for those still on anticoagulation at this time; ~ only ECS logs; ** \$25 at Visit 1 and 2, and \$50 at Visit 3; ***Medication logs only for participants on Rivaroxaban or Xarelto; ^^Factor VIII, D-dimer, and CRP can be completed as research procedures at Visit 3 for participant's whose values were within normal range at Visit 2.

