Subjects will be asked to maintain the target steps/day for a period of 8 weeks. At the end of this period, subjects will either maintain the increased activity or resume habitual activity for another 4 weeks, per patient preference. A phone call will be made periodically for encouragement and to ensure adherence to the activity regimen throughout the initial 16-week period. Subjects will have another visit 8 weeks (± 4 weeks) after the end of the 16-week period corresponding to the ~ 9 month post-diagnosis SOC visit. For subjects having difficulty with the activity prescription or use of the Fitbit, a phone call or face-to-face session will be arranged with the study research coordinator and physical therapist. Such changes will be carefully documented.

2. **Control arm.** The control intervention will consist of:
 - 1) a standardized 15-20 minute education session on PTS (what constitutes PTS, why patients get it, how to manage it) and benefits of enhanced activity

(activity will not be specifically addressed and will be up to the choice of the subject) after DVT; 2) monthly phone contacts will be made to check in with patients/families and remind them about completion of activity logs and follow-up visits.

Study assessments for both arms

1. Biomarker testing: Blood for biomarker of coagulation activation (D-dimer, FVIII, thrombin generation), markers of inflammation (CRP), and markers of fibrinolysis {modified thromboelastogram (TEG) with fibrinolysis, PAI-1, will be obtained at each visit One and a half extra teaspoons will be collected at each visit for a total of 4.5 teaspoons collected during the subject's time in the study.}
2. Elastic compression stockings (ECS)
 - i. Subjects in both arms will be provided with custom fitted compression stockings and their use will be tracked using ECS logs throughout study period. In general, SOC recommendations are to wear ECS starting after the diagnosis of DVT and to continue as long as they provide benefit in regards to pain and swelling, up to a period of two years post DVT diagnosis. For the sake of the study, their use will be documented strictly during the study period.
3. Activity log completion during the intervention period will be used to record physical activities. These logs will capture information on the type of activity, and the frequency and duration of activity

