Analyses: The objectives of this trial are to assess the feasibility of the design and to measure the effect size of the intervention. All analyses will therefore be descriptive and will be performed once, at the end of the trial. Means and standard deviations, or when appropriate, medians and semi-inter-quartile ranges will be used to describe demographic and clinical characteristics. Reasons for non-eligibility, lack of consent, dropout and lack of compliance will be documented. For feasibility indicators, we (study investigators and [name]-biostatistician) will describe rate of eligibility (proportion of subjects screened who fully meet trial eligibility criteria to participate in the trial), rate of consent (the proportion of eligible subjects who consent to participate) and rate of loss to follow-up (proportion of randomized subjects who drop out of the trial, in total, and by allocated intervention). We will also describe the level of compliance in the intervention group, calculated as the ratio of who complied with the activity prescription to the number given the prescription. We will consider the trial *successful* if the following criteria are met: rate of eligibility $\geq 30\%$, rate of consent $\geq 30\%$, rate of loss of follow-up $<20\%$, level of compliance $\geq 60\%$ and proportion of subjects who complete the trial $\geq 80\%$. For the clinical outcomes (including the secondary outcomes), we will describe change (means and standard deviations) in the intervention and control groups, from baseline to 6 month, in the QoL scores and PTS biomarkers. Each change score will be interpreted for clinical significance and common responses counted for frequency of occurrence. The impact of the activity

Table 2: Feasibility Indicators

Proportion of screened subjects who meet eligibility criteria: $\geq 30\%$

Proportion of screened subjects who provide consent: $\geq 30\%$

Level of adherence in the intervention arm: $\geq 60\%$

Proportion of subjects who complete the trial: $\geq 80\%$

tracker to promote continued physical activity in the last 2 weeks of the 12-week period would be explored. We will also assess the impact of covariates such as age, sex, BMI, baseline activity, intensity of activity over and above the activity prescription, on change scores.

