using mean (standard deviations [SD]) for continuous outcomes, and raw counts (%) for categorical outcomes are reported. For the clinical end points, using an intent-to-treat analysis that includes all participants with data at baseline and 6 months (end of the intervention period), within-patient change from baseline (diagnosis or pre-VTE levels) to 6 months (mean, SD) in the physical activity will be compared to standard care in the following measures: D-dimer, FVIII, CRP, thrombin generation assay parameters of endogenous thrombin potential and peak thrombin, fibrinolysis on thromboelastography, QoL (total and physical), selfreported physical activity levels, and PTS (change from 6 to 9 months). This will be averaged for each group, and within-group differences will be compared between the standard care and physical activity groups using a t test. ECS use will be descriptively described but not included in a formal analysis.

ETHICS AND DISSEMINATION

I. RESEARCH ETHICS APPROVAL

This protocol and template informed consent forms will be reviewed and approved UT Southwestern IRB with respect to scientific content and compliance with applicable research and human subjects regulations. Subsequent to initial review and approval, the investigators will submit progress reports to the IRB at least annually and at study closure.

II. PROTOCOL AMMENDMENTS

Any modifications to the protocol, which impact the conduct of the study, or potential risk/benefit of the participants, will require a formal amendment to the protocol with IRB approval.

III. CONSENT OR ASSENT

Informed consent will be obtained after information has been provided to patients' families along with a discussion of the risks and benefits along with opportunity for questions. Consent forms will be provided for all parents involved in the trial.

IV. CONFIDENTIALITY

Records of each patient's participation in this study, including the original informed consent document, will be kept in a locked file cabinet in the Center for Cancer and Blood Disorders at Children's Medical Center. Access to local

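### The hypothesis that the tracker improves adherence cannot be tested, because adherence is defined and measured only in the Fitbit arm

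*Combined protocol and SAP*

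**What the plan says.** The primary aim reads: "To demonstrate the feasibility and potential effectiveness of a personal “fitness tracker” to improve adherence to an activity regimen following an initial DVT in children". The hypothesis beneath it adds: "The intervention of using a fitness tracker to adhere to an activity regimen will be acceptable, and effective in improving adherence". The Study Design section sets the tracker "against standard practice, which currently consists of providing education about PTS and instructions to 'be active", and subjects are "individually randomized via a web-based program to the Fitbit arm or the control arm (1:1 allocation ratio".

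In the Fitbit arm (Study Protocol, Schedule and procedures), subjects wear the device for four weeks to establish habitual steps. They then receive an individual daily step target "corresponding to a 25% increase above the baseline", to be held for 8 weeks. For the control arm, "activity will not be specifically addressed and will be up to the choice of the subject".

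On measurement, the Analyses paragraph of Outcomes and Power Calculations says: "We will also describe the level of compliance in the intervention group". Table 2 sets the threshold at 60% or more in that arm. Under Statistical Analyses, one of about ten measures whose change is compared between arms by t test is "selfreported physical activity levels".

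**The concern.** Improvement is a comparative claim, so it needs a reference value: a control-arm rate, or a rate in the same subjects without the tracker. The plan appears to supply neither. The adherence result will be one percentage from one arm, and randomisation plays no part in it.

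The pilot is meant to inform a definitive trial. If a rate of 60% or more were taken as confirming the hypothesis, that trial would start from an effect on adherence that was never estimated.

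**Working it through.** **1. Where adherence is defined.**

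| Place | Who is counted | Reference value |
|---|---|---|
| Outcomes and Power Calculations, primary outcomes | Fitbit arm, meeting the step goal in the 8 active weeks | none |
| Analyses | Fitbit arm, compliers over those given the prescription | none |
| Table 2 | Fitbit arm, at least 60% | fixed threshold |
| Statistical Analyses | Fitbit arm, those who adhered | none |
| Table 1, steps/day data | listed for Fitbit subjects only | none |
| Control arm | no target, no steps data | adherence undefined |

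**2. Could the subject's own baseline serve?** The target is 25% above each subject's four-week step count, so meeting it is by construction a rise over recorded activity. But that count is taken while the tracker is worn, and the comparison is not randomised. It cannot separate an effect of the tracker from the target, the calls or recovery over time.

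**3. What the 60% criterion can show.** Assume each subject is classed as adherent or not (the plan does not say how many of the 8 weeks must meet the goal), with 20 or 22 subjects in the arm (Sample size calculation). The smallest passing counts are 0.60 × 20 = 12, and 0.60 × 22 = 13.2, so 14. The exact 95% limits are the 2.5% point of Beta(r, n − r + 1) and the 97.5% point of Beta(r + 1, n − r):
- 12/20 = 60.0%: 36.1% to 80.9%
- 14/22 = 63.6%: 40.7% to 82.8%

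The chance of passing is P(X ≥ r) for X binomial(n, p):

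| True adherence | n = 20, r = 12 | n = 22, r = 14 |
|---|---|---|
| 50% | 25% | 14% |
| 60% | 60% | 45% |
| 70% | 89% | 81% |
| 80% | 99% | 98% |

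These figures describe a one-sample rule. The width of the intervals is small-sample imprecision and would be there with or without a control rate. The fault lies in the table in step 1.

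**4. The plan's only power figure.** It states a 71% chance of p < 0.2 if PTS risk falls from 26% to 10%. With 22 per arm and pooled risk 0.18:
- null SE = √(2 × 0.18 × 0.82 / 22) = 0.1158
- alternative SE = √((0.26 × 0.74 + 0.10 × 0.90) / 22) = 0.1133
- one-sided: (0.16 − 0.8416 × 0.1158) / 0.1133 = 0.55, giving 70.9%

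The figure reproduces as a one-sided test (54.1% two-sided). It concerns PTS and says nothing about adherence or activity.

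**5. The randomised activity contrast that does exist.** Self-reported activity is compared between arms, but it is not named among the primary outcomes in either Primary Aim or Outcomes and Power Calculations. No instrument is named. Appendix 5 holds a leisure-time exercise questionnaire, fields for a second activity score (PAQ-C/PAQ-A) and activity-level categories, and both arms also keep activity logs.

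**6. Timing.** Four baseline weeks + 8 active weeks + 4 optional weeks = 16 weeks. Visit 2 is scheduled 16 weeks after Visit 1, with a window of 16 − 4 = 12 to 16 + 4 = 20 weeks. On schedule, a Visit 2 questionnaire about a typical week follows four weeks in which subjects may have gone back to habitual activity. The logs cover the active weeks directly.

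**7. Baseline.** Statistical Analyses takes baseline as the level at diagnosis or before the VTE. For activity, a change from that point mixes the effect of the clot itself with anything that follows randomisation. Table 1 schedules the questionnaire for all subjects at Visit 1.

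**The case against.** The strongest reply is that this is a pilot. The aim speaks of feasibility and potential effectiveness, the analyses are declared descriptive, and the plan admits that its size limits validity. A single-arm adherence rate with a preset threshold is a normal feasibility indicator. All of that stands, and nothing here asks for the 60% criterion to be dropped. A descriptive analysis still needs a contrast before it can describe improvement.

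A reader might infer more than the documents support:
- *That the design cannot show any improvement, or fails its primary question altogether.* Study Design speaks of increasing activity against standard practice, and Statistical Analyses compares self-reported activity between the randomised arms. The gap is specific to adherence, and the feasibility questions can be answered.
- *That the sponsor plans to present 60% or more as proof that the tracker works.* No section does so. The threshold is one of several criteria for calling the trial successful.
- *That failing to isolate the tracker is a design error.* The background describes trackers used together with step goals and incentives, and separating the components is not a stated aim. What remains is that the aim and hypothesis name the tracker alone, while the arm also receives an individual target and, in Table 1, weekly calls (the text says only that calls are periodic) against monthly calls for controls.

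**Conclusion.** The hypothesis of improved adherence cannot be tested with adherence as the plan defines it. Every definition is confined to the Fitbit arm, controls have nothing to adhere to, and the step baseline is not tracker-free. The size of the problem is structural: there is no adherence contrast to estimate, at any sample size. The 60% criterion remains valid for feasibility, with an interval of roughly 36% to 81% at 12/20.

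What the trial can estimate is a between-arm difference in self-reported activity for the package. With 20 per arm its 95% half-width is about 1.96 × √(2/20) = 0.62 standard deviations (0.59 at 22 per arm), by normal approximation and before any gain from baseline adjustment. That is wide, but it is a randomised estimate, and the plan should give it a defined place.

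This rests on reading Table 1 literally, so that steps data are collected in the Fitbit arm only, and on logs being kept in both arms as the assessments section states.

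**What to change.** 1. Reword the aim and hypothesis to acceptability plus adherence within the Fitbit arm, reported with an exact 95% CI against 60%.
2. State that any between-arm difference in activity concerns the package (tracker, individual target, weekly calls) versus education with monthly calls.
3. Pre-specify one lead between-arm activity estimate with a 95% CI, adjusted for the Visit 1 questionnaire score. Take it from the activity logs over the 8-week active period, using the same calendar weeks in controls, and name the summary (for example, mean recorded minutes per week, since the logs capture frequency and duration). Keep the Visit 2 leisure-time questionnaire score as supportive, because on schedule it follows the optional 4-week return to habitual activity. Report log completion by arm.
4. For the activity analysis, use Visit 1 as baseline in place of the level at diagnosis or before the VTE.

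The cost is protocol and SAP wording, with no new data or visits. The downside is a narrower claim, and a lead activity measure that is self-reported, unblinded and dependent on log completion.

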Venous thromboembolism (VTE) is a major and growing problem in children. A 70% increase in the annual rate of VTE in hospitalized children has been documented in the past decade[1]. VTE often collectively referred to as deep venous thrombosis (DVT) and pulmonary embolism (PE), is now considered an important endemic complication of tertiary care settings. Although often perceived as an acute disorder, VTE entails a long-term risk of persistent or progressive thrombosis, post-thrombotic syndrome (PTS), recurrence and post-PE syndrome, also called chronic thromboembolic pulmonary hypertension (CTEPH)[2]. Of all the VTE outcomes, PTS is the most frequent, chronic and debilitating complication[3]. As such, current therapy is merely focused on treating the acute VTE, not attempting to prevent late sequelae like PTS. Despite appropriate anticoagulation, up to one half patients will develop these poor complications within 2 years of the acute event[4].

VTE is not merely a 'nuisance' medical problem. *Rather, VTE is costly and burdensome to patients and society*, both in terms of dollars spent and effect on quality of life and productivity[5]. The estimated health care costs directly attributable to pediatric VTE for care of secondary VTE are five times higher than costs with an idiopathic VTE (\$95,120 vs. \$20,238)[5]. These costs are expected to be much higher in the presence of adverse outcomes of thrombosis[6].

Although **PTS is a direct and most frequent DVT complication in children, effective treatments are lacking and new innovative approaches to manage PTS are sorely needed**. The 9th edition of the American College of Chest Physicians (ACCP) guidelines on antithrombotic Therapy in Neonates and Children, widely considered to represent the standard of care for pediatric thrombosis do not currently have any recommendations for management of pediatric PTS[7]. Recently, the American Heart Association issued a scientific statement to provide an up-to-date overview of PTS and concluded, "*as a result of the paucity of studies in this area, it is not possible to make specific recommendations on the prevention or treatment of pediatric PTS*", highlighting this as an area in pressing need of scientific investigation[8]. Despite receiving early detection and appropriate anticoagulation, up to a quarter to one half of DVT patients develop PTS[3]. Lack of effective and evidence-based treatment for PTS is a

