Sample size calculation: For reasons of practicality and cost, we have decided to limit the size of this pilot RCT to 44 subjects (20 in each arm; 22 after considering a 20% drop out rate). We anticipate that the probable primary outcome for the larger trial will be change in rate of PTS development and/or progression. This trial may also provide compelling preliminary data for future studies. For example, if this intervention reduces the risk of PTS from 26% (known probability of PTS) to 10%, this pilot study has 71% chance of showing a promising trend (p-value<0.2) that the intervention reduces the risk of PTS. We acknowledge that the small size of this pilot study limits the validity of the findings; therefore, we will be cautious with such analyses.

I. RECRUITMENT

- a. Information about the clinical study will be provided via direct communication by study investigators and physicians at Children's Medical Center including ED physicians, hospitalists, and general pediatricians attending on the inpatient medicine services and outpatient continuity clinic as well as house officers.
- b. Information regarding the study will be available on the University of Texas Southwestern clinical trials website and at clinicaltrials.gov.
- c. Potential subjects will be identified through review of new patient referrals to Children's Medical Center, inpatient admissions and/or consultations for thrombosis.
- d. Each subject will receive financial compensation for participation. Payment will be made at completion of the study visits at Visits 1 and 2 (\$25 each) and at the end of Visit 3 (\$50) based on attendance and return of the tracking logs.
- e. Expected recruitment rate will be 2-3 participants per month.
- f. Duration of recruitment period is expected to be approximately 24 months.

- g. Assessment of study recruitment and retention will be performed when 20 participants have been enrolled on the study, or at approximately 9 -12 months.

II. DATA COLLECTION, MANAGEMENT AND ANALYSIS

a. DATA COLLECTION METHODS

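### Inclusion 2 admits pulmonary embolism without leg DVT, while the rest of the plan describes a DVT population and no PTS analysis set is defined, so PE-only subjects would probably dilute the PTS results

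*Combined protocol and SAP*

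**What the plan says.** **Who may enter.** Section II (Eligibility Criteria), inclusion 2, joins the two index events by and/or: "first lower extremity DVT and/or confirmed", continuing "acute pulmonary embolism (unilateral or bilateral"). PE alone is enough. The rationale cell gives the reason: "Population with proximal DVT and/or PE deemed to be at highest risk of PTS".

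**Who is described elsewhere.** Section I (Study Setting) says who will be approached: "All newly diagnosed patients with first, lower extremity DVT". The hypothesis under Primary Aim describes a pilot "in which 44 subjects with DVT will be assigned to the intervention group or to a comparison group". Table 1 times Visit 1 from the DVT diagnosis, and the baseline-assessment item on PTS (section III.a.v) starts PTS scoring at 6 months from that same diagnosis.

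**What PTS is taken to be.** The introduction states "PTS is a direct and most frequent DVT complication in children" and lists post-PE syndrome as a separate late outcome. Both scales in Appendix 1 rest mainly on limb findings.

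**Who is analysed for PTS.** Section III.a.v applies the scales to all subjects, and Table 1 lists PTS assessment under all subjects. Statistical Analyses uses an intent-to-treat set of everyone with baseline and 6-month data, with PTS (change from 6 to 9 months) among the measures compared by t test. No sentence limits PTS to subjects with leg DVT.

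**What the numbers assume.** The sample size paragraph supposes that the intervention "reduces the risk of PTS from 26% (known probability of PTS) to 10" percent, and gives a 71% chance of p<0.2. It names PTS development or progression as the probable primary outcome of the larger trial.

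**The concern.** The eligibility table and the rest of the plan describe different populations. A PE-only subject has no DVT diagnosis date from which to time visits and no affected leg to score, yet is scored on both scales and enters the PTS comparison.

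If such subjects rarely develop PTS, they lower the PTS frequency in both arms and narrow the difference. If they score positive because of unrelated limb symptoms, they add events that treatment of a leg DVT could not change, and the difference narrows as well. Either way the pilot hands the larger trial a PTS rate and an effect that mix two groups in an unknown proportion. The 71% also assumes that 26% applies to every randomised subject, and the plan does not say which patients the 26% comes from.

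**Working it through.** **Inputs from the plan.** PTS risks 26% and 10%; threshold p<0.2; 44 subjects allocated 1:1, so 22 per arm (20 per arm after dropout); stated chance 71%. The plan gives neither the test nor its sidedness.

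**Assumptions.** PE-only share *f* = 20% or 40%, equal in both arms. PTS risk *r* in PE-only subjects is 0 at first, then 5% or 10% in both arms.

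**Step 1: reproduce the 71%.** For two proportions, one-sided 0.2 (z = 0.8416):

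power = Φ{ [d − z·√(2·p̄·(1−p̄)/n)] / √([p₁(1−p₁) + p₂(1−p₂)]/n) }

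With n = 22, d = 0.16 and p̄ = 0.18:
- null standard error √(2×0.18×0.82/22) = 0.1158
- alternative standard error √((0.1924 + 0.0900)/22) = 0.1133
- (0.16 − 0.8416×0.1158)/0.1133 = 0.552, so power = 70.9%

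This matches the stated figure. The same formula at 20 per arm gives 68.7%, and exact enumeration of the pooled z test at 20 per arm gives 70.7%. A two-sided test gives 51.4% (20 per arm) or 54.1% (22 per arm), so the 71% needs a one-sided test.

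**Step 2: leave PE-only subjects in, r = 0.** Each risk is multiplied by (1 − f):
- f = 20%: 26% × 0.8 = 20.8% and 10% × 0.8 = 8.0%; the difference falls from 16 to 12.8 points
- f = 40%: 26% × 0.6 = 15.6% and 10% × 0.6 = 6.0%; the difference is 9.6 points

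**Step 3: analyse PTS in DVT subjects only.** The risks stay at 26% and 10%, and n becomes 22 × 0.8 = 17.6 or 22 × 0.6 = 13.2 per arm.

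| PE-only share | All subjects, r = 0 | DVT subjects only |
|---|---|---|
| 0% | 70.9% | 70.9% |
| 20% | 64.6% | 65.6% |
| 40% | 57.4% | 59.2% |

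The gain in power from restriction is only 1 to 2 points. The gain in interpretation is larger: the expected difference returns to 16 points in a defined population.

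**Step 4: does a PTS risk above zero in PE-only subjects rescue the figure?** Risks become (1 − f)×26% + f·r and (1 − f)×10% + f·r. If r is the same in both arms, the difference is unchanged from Step 2 while the variance rises:
- f = 20%: power 63.3% (r = 5%) and 62.2% (r = 10%), against 64.6% at r = 0
- f = 40%: power 54.5% and 52.2%, against 57.4% at r = 0

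The loss shrinks only if the intervention also lowers PTS in PE-only subjects.

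**The case against.** The strongest reply is that PE was admitted deliberately. The rationale for inclusion 2 names PE, so a reader who calls the criterion a slip is contradicted by the next cell. That stands. The rationale does not resolve the conflict, however: the setting, the aim and the visit clock still say DVT, and the introduction offers no support for PTS after PE alone.

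A reader might infer that the population, the scales and the 26% all concern leg DVT. The documents do not go that far. The rationale includes PE. The Manco-Johnson form lists superior vena cava syndrome and the modified Villalta score lists head swelling, so the scales are mainly but not wholly limb-based, and not leg-only. The 26% carries no source or population; the nearest text, a quarter to one half, refers to DVT patients generally.

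The size is also uncertain. If only DVT patients are approached, as Study Setting says, the PE-only share could be zero. The plan defines no PTS proportion or denominator; that PE-only subjects are counted follows from the all-subjects and intent-to-treat wording, not from an explicit sentence. If the larger trial kept the same criterion, a mixed rate could be the relevant input, but the plan does not say so, and a mixed rate is of use only when its components are known.

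Finally, little in this pilot depends on PTS. It is the secondary outcome, analyses are described as descriptive, the sample size was set by practicality and cost, the 71% is introduced as an example, and the plan promises caution. This limits the severity and does not remove the point.

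**Conclusion.** The inconsistency is real: inclusion 2 admits PE without leg DVT, the plan otherwise describes DVT subjects, and no PTS analysis set is defined. The consequence is conditional. With a PE-only share of 20% to 40% and no PTS risk in that group, the illustrative difference falls from 16 points to 12.8 or 9.6, and the 71% to about 65% or 57%. Both the share and the risk are assumptions. With no PE-only subjects nothing changes.

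Two stronger conclusions are tempting and unsupported. One is that the 71% is correct for the DVT subjects: it is not unless all 44 have DVT, since the DVT subset alone gives about 66% or 59%. The other is that the trial's main results are compromised: the feasibility, QoL and biomarker outcomes do not use the PTS denominator. The point is minor to moderate.

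**What to change.** 1. Reconcile inclusion 2 and its rationale with Study Setting, the Primary Aim, the count of 44 subjects with DVT, and visit times that run from DVT diagnosis. This point takes no view on which population is right, and the analysis changes below need no change to enrolment.
2. Define the main PTS analysis set as randomised subjects with leg DVT confirmed at baseline. Report PE-only subjects separately, and show the all-randomised PTS result alongside. Membership rests on a baseline fact, and section III.a.iv already collects site and venous segments at diagnosis.
3. Keep every randomised subject in the feasibility, QoL and biomarker analyses.
4. State the source population of the 26%. Say that the 71% holds only if all 44 subjects have DVT, and is lower otherwise.

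The cost is protocol and SAP wording, with no new data. The downside is a smaller main PTS table: at a 20% share, 22 × 0.2 = 4.4, or about 4 fewer subjects per arm. The all-randomised result shown beside it keeps that information.
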